15.2. Ethical Conduct of the Study

The investigator agrees, when signing the protocol, to conduct the study in accordance with ethical principles that have their origin in the current revision of the Declaration of Helsinki and are consistent with ICH/GCP, applicable regulatory requirements, and policies and procedures as outlined by the ethical requirements for IRB or IEC review and ICDs.

The Investigator agrees to allow monitoring and auditing of all essential clinical study documents by the Sponsor or its authorized representatives and inspection by the FDA, EMA, or other appropriate regulatory authorities. Monitoring and auditing visits by the Sponsor or

authorized designee will be scheduled with the appropriate staff at mutually agreeable times periodically throughout the study.

The Investigator will assure proper implementation and conduct of the study, including those study-related duties delegated to other appropriately qualified individuals. The Investigator will assure that study staff cooperates with monitoring and audits, and will demonstrate due diligence in recruiting and screening study patients. The Investigator must sign and return to the Sponsor the “Investigator’s Signature” page (see [Appendix 3](#)) and provide a copy of current curriculum vitae. For this study and all studies conducted under an IND, the Investigator must sign and return a completed Form FDA 1572 “Statement of Investigator” to the Sponsor (or designee). For European Union (EU) investigators, equivalent information contained within the FDA 1572 form may be requested unless a waiver has been requested and received by the Sponsor from the FDA.

15.3. Written Informed Consent

The Principal Investigator(s) at each center will ensure that the patient is given full and adequate oral and written information about the nature, purpose, possible risk and benefit of the study. Patients must also be notified that they are free to discontinue from the study at any time. The patient should be given the opportunity to ask questions and allowed time to consider the information provided.

The patient’s signed and dated informed consent must be obtained before conducting any study procedures.

A separate informed consent will be obtained for collecting the genetic blood sample.

The Principal Investigator(s) must maintain the original, signed ICD. A copy of the signed ICD must be given to the patient.

15.4. Patient Confidentiality

The names and identities of all research patients will be kept in strict confidence and will not appear on eCRFs or other records provided to or retained by the Sponsor (or the Sponsor’s authorized representative). If a patient’s name appears on any document, it must be redacted and replaced with the patient identifier before a copy of the document is supplied to the Sponsor or Sponsor’s authorized representative. The ICD must include appropriate statements explaining that patient data will be confidential and what actions will be taken to ensure patient confidentiality.

Any other confidentiality requirements specified by the site, IRB or IEC, or national or local regulations will be adhered to and detailed appropriately in the ICD.

16. DATA HANDLING AND RECORDKEEPING

16.1. Inspection of Records

Applicable regulations require the Sponsor (or the Sponsor's authorized representative) to inspect all documents and records to be maintained by the Investigator, including but not limited to, medical records (office, clinic, or hospital) for the patients in this study. These regulations also allow the Sponsor's records to be inspected by authorized representatives of the regulatory agencies. The Investigator will permit study-related monitoring, audits, IRB or IEC review, and regulatory inspections by providing direct access to source data/documents. Direct access includes permission to examine, analyze, verify, and reproduce any records and reports that are important to the evaluation of a clinical study.

16.2. Retention of Records

In compliance with the ICH/GCP guidelines, the Investigator/Institution agrees to retain and maintain all study records that support the data collected from each patient, as well as all study documents as specified in ICH/GCP, Section 8 Essential Documents for the Conduct of a Clinical Trial. The Investigator agrees to contact the Sponsor before destroying or relocating any study documentation and is expected to take measures to prevent accidental or premature destruction of these documents.

If the Investigator retires, relocates, or for other reasons withdraws from the responsibility of keeping the study records, custody must be transferred to a person who will accept responsibility. The Sponsor must be contacted in writing regarding the name and address of the new person responsible as well as the disposition of document storage. Under no circumstances shall the Investigator relocate or dispose of any study documents before having obtained written approval from the Sponsor.

Essential records (including eCRFs, source documents, study drug disposition records, signed patient ICDs, AE reports, and other regulatory documents) as required by the applicable regulations, must be maintained for 2 years after a marketing application is approved for the drug for the indication for which it is being investigated; or, if no application is to be filed or if the application is not approved for such indication, until 2 years after formal discontinuation of clinical development of the investigational product.

It is the responsibility of the Sponsor to inform the Investigator/Institution as to when these documents no longer need to be retained.

16.3. Case Report Forms and Study Records

Access to eCRFs will be provided to the clinical site. As part of the responsibilities assumed by participating in the study, the Investigator agrees to maintain adequate case histories for the patients treated as part of the research under this protocol. The Investigator agrees to maintain accurate source documentation and eCRFs as part of the case histories.

Study records are comprised of source documents, eCRFs, and all other administrative documents (eg, IRB or IEC correspondence, clinical study materials and supplies shipment manifests, monitoring logs, and correspondence). A study-specific binder will be provided with instructions for the maintenance of study records.

Source documentation is defined as any handwritten or computer-generated document that contains medical information or test results that have been collected for or in support of the protocol specifications (eg, laboratory reports, clinic notes, study drug disposition log, pharmacy records, patient sign-in sheets, patient completed questionnaires, telephone logs, x-rays, and ECGs). All draft, preliminary, and pre/final iterations of a final report are also considered to be source documents (eg, faxed and hard copy of laboratory reports, faxed and hard copy of initial results, and final report).

The Investigator agrees to allow direct access to all essential clinical study documents for the purpose of monitoring and/or auditing by the Sponsor or its authorized representatives and inspection by the appropriate regulatory authorities.

Data reflecting the patient's participation with the study drug under investigation are to be reported to the Sponsor. The data are to be recorded on the eCRFs and/or other media provided or approved by the Sponsor.

A completed eCRF must be submitted for each patient who receives study drug, regardless of duration. All supportive documentation submitted with the eCRF, such as laboratory or hospital records, should be clearly identified with the study and patient number. Any personal information, including patient name, should be removed or rendered illegible to preserve individual confidentiality. The eCRF should not be used as a source document unless otherwise specified by the Sponsor.

Neither the Sponsor nor a service provider contracted to analyze data and complete the study report is permitted to interpret a blank answer; therefore, all fields should be completed. All requested information must be entered on the eCRFs. If an item is not available or is not applicable, this fact should be indicated as not available (N/A) or not done (N/D); do not leave a field blank.

Each set of completed eCRFs must be signed and dated by the Investigator acknowledging review and that the data are accurate and complete. The completed database is to be returned to the Sponsor as soon as practical after completion by the mechanism prescribed for the protocol.

It is essential that all dates appearing on the Sponsor's patient data collection forms for laboratory tests, cultures, etc, be the dates on which the specimens were obtained or the procedures performed. The eCRFs will be electronically signed by the Investigator and dated as verification of the accuracy of the recorded data. All data collection forms should be completed within a timely manner according to the CRF completion guidelines.

17. ADMINISTRATIVE CONSIDERATIONS

17.1. Investigators

The Investigator must agree to the responsibilities and obligations listed below, as specified by the appropriate FDA/EMA regulatory requirements or ICH/GCP guidelines:

- Agree to conduct the study in accordance with the relevant current protocol
- Agree to personally conduct or supervise the described investigation(s)
- Agree to inform any patients, or persons used as controls, that the study drugs are being used for investigational purposes and ensure that the requirements relating to obtaining informed consent and IRB/IEC review and approval are met
- Agree to report adverse experiences that occur during the course of the investigation(s)
- Read and understand the information in the IB, including the potential risks and side effects of the study drug
- Ensure that all associates, colleagues, and employees assisting in the conduct of the study are informed about their obligations in meeting the above commitments
- Maintain adequate and accurate records and make those records available for inspection
- Ensure that an appropriate IRB/IEC will be responsible for the initial and continuing review and approval of the clinical investigation
- Agree to promptly report to the IRB/IEC all changes in the research activity and all unanticipated problems involving risks to patients or others
- Agree to not make changes in the research without IRB/IEC approval, except where necessary to eliminate apparent hazards to patients
- Comply with all other requirements regarding the obligations of clinical Investigators and all other pertinent requirements.
- Refer also to:
 - FDA Regulations Related to GCP and Clinical Trials:
<http://www.fda.gov/oc/gcp/regulations.html>
 - Guidance and Information Sheets on GCP in FDA-Regulated Clinical Trials:
<http://www.fda.gov/oc/gcp/guidance.html>
 - Guidance for IRBs and Clinical Investigators:
<http://www.fda.gov/oc/ohrt/irbs/default.htm>
 - DIRECTIVE 2001/20/EC:
http://ec.europa.eu/health/files/eudralex/vol-1/dir_2001_20/dir_2001_20_en.pdf

- Guidance for Industry – E6 Good Clinical Practice: Consolidated Guidance:
<http://www.fda.gov/cder/guidance/959fnl.pdf>

17.3. Amendments

Changes to the research covered by this protocol must be implemented by formal protocol amendment. All amendments to the protocol must be initiated by the Sponsor and signed and dated by the Investigator. Protocol amendments must not be implemented without prior IRB or IEC approval. Documentation of amendment approval by the Investigator and IRB or IEC must be provided to the Sponsor or its authorized representative. When the change(s) involve only logistic or administrative aspects of the study, the IRB or IEC only needs to be notified.

During the course of the study, in situations where a departure from the protocol is unavoidable, the Investigator will contact the Medical Monitor. Except in emergency situations, this contact should be made before implementing any departure from the protocol. In all cases, contact with the Medical Monitor must be made as soon as possible to discuss the situation and agree on an

appropriate course of action. The data recorded on the eCRF and source documents will reflect any departure from the protocol and the source documents will describe the departure and the circumstances requiring it.

17.4. Financial Disclosure

Prior to the start of the study, Investigators will release sufficient and accurate financial information that permits the Sponsor to demonstrate that an Investigator and all study relevant assigned personnel have no personal or professional financial incentive regarding the future approval or disapproval of the study drug such that his or her research might be biased by such incentive.

18. PUBLICATION AND DISCLOSURE POLICY

It is understood by the Investigator that the information and data included in this protocol may be disclosed to and used by the Investigator's staff and associates as may be necessary to conduct this clinical study.

All information derived from this clinical study will be used by the Sponsor (or designee) and therefore, may be disclosed by the Sponsor (or designee) as required to other clinical Investigators, to the FDA, EMA, and to other government agencies, or in connection with intellectual property filings or publications. In order to allow for the use of the information derived from this clinical study, it is understood by the Investigator that there is an obligation to provide the Sponsor with complete test results and all data from this clinical study. The Investigator agrees to maintain this information in confidence, to use the information only to conduct the study, and to use the information for no other purpose without the Sponsor's prior written consent (or as otherwise may be permitted pursuant to a written agreement with the Sponsor or its designee).

The results of the study will be reported in a clinical study report prepared by the Sponsor (or designee), which will contain eCRF data from all clinical sites that conducted the study.

The Sponsor shall have the right to publish data from the study without approval from the Investigator. Manuscript(s) and abstract(s) may only be prepared through cooperation between the Sponsor (or designee) and the study Investigator(s). If an Investigator wishes to publish information from the study, a copy of the manuscript must be provided to the Sponsor for review in accordance with the provisions of such Investigator's written agreement with the Sponsor (or designee) before submission for publication or presentation. If requested by the Sponsor in writing, the Investigator will withhold such publication in accordance with the provisions of such agreement.

APPENDIX 1. SCHEDULE OF EVENTS (SUBJECT VISIT SCHEDULE)

	Screen	Run-in		Treatment						
Visit	S1 ^{1,2}	S2	S3	T1	T2	T3/phone	T4	T5	T6/phone	T7/EOS ³
Week	Wk -5	Wk -4	Wk -1	Wk 0	Wk 4	Wk 8	Wk 12	Wk 24	Wk 36	Wk 52
Procedure	Day -35±7	Day -28±3	Day -7±3	Day 1	Day 29±3	Day 57±3	Day 85±3	Day 168±7	Day 252±7	Day 365 ±7
Informed Consent	X									
Enrollment Criteria	X									
Demographics	X									
Medical History	X									
HeFH Status Determination	X									
Concomitant Medications	X	X	X	X	X	X	X	X	X	X
Adverse Event Recording		X	X	X	X	X	X	X	X	X
Physical Exam				X						X
Weight ⁴	X			X	X		X	X		X
Height/BMI	X									
12-Lead ECG ⁵				X						X
Vital Signs ⁶	X	X	X	X	X		X	X		X
Serology ⁷	X									
Serum Pregnancy and/or FSH ⁸	X									
Urine Pregnancy Test ⁸				X						
TSH	X									
Clinical Safety Labs ⁹	X			X	X		X	X		X
Basic Fasting Lipids ¹⁰	X		X	X	X		X	X		X
HbA _{1c}	X			X			X	X		X
apoB				X			X	X		X
hs-CRP				X			X	X		X
Diet and exercise counseling ¹¹	X	X	X	X	X	X	X	X	X	X
Plasma PK								X		X
Establish Patient Eligibility				X						
Randomization				X						
IWRS Contact	X	X		X			X	X		X ¹²
Single-Blind Drug Dispensing		X								
Double-blind Drug Dispensing ¹³				X			X	X		
Drug Return/Compliance			X	X	X		X	X		X
Schedule next visit	X	X	X	X	X	X	X	X	X	

NOTE: For patients who withdraw from IMP treatment, they will continue to have visits according to the protocol schedule. Safety assessments should include clinical safety and basic lipid laboratories (except for apoB and hs-CRP), adverse events, PE, vital signs, and ECGs. For patients who withdraw from IMP treatment, but refuse to come to the clinic for assessments, assessments will take place by phone. The telephone contacts will occur according the protocol schedule with information regarding current health status and to collect information on AEs (eg, recent procedures, hospitalizations, and if the patient has died, the cause of death).

- ¹ An optional visit between Visits S1 and S2 may be completed if patient fails to meet TG entry criterion. If this optional basic fasting (minimum of 10 hours) lipid value visit is completed, the repeat lipid value will be used to determine eligibility.
- ² An optional visit between Visits S1 and S2 may be completed if the patient's DBP and/or SBP meet the exclusion criteria levels. Patients may randomize after blood pressure medications have been adjusted, the patients have been on stable doses of blood pressure medications for at least 2 weeks, and the repeat blood pressure values (DBP and/or SBP) do not meet exclusionary values. An optional visit between Visit S1 and S2 may be completed to determine eligibility if the patient's eGFR, ALT, AST, and/or TB meet exclusion criteria levels. If this optional visit is completed, the repeated value will be used to determine eligibility.
- ³ All procedures will be completed for all patients at either End of Study (EOS) if completing the study or early withdrawal.
- ⁴ Body weight will be measured while fasting, using consistent scales, after voiding, and without shoes and outerwear (eg, coats).
- ⁵ Single 12-lead ECG will be collected prior to any blood sample collection.
- ⁶ Vital signs will include DBP, SBP, and HR and will be collected prior to any blood sample collection. Patient will rest for 5 minutes prior to assessments
- ⁷ Serology for HBsAg, HCV
- ⁸ Serum pregnancy test completed in premenopausal women only. FSH test is completed in women <55 years old and >1 year without menses. Urine pregnancy test in women of childbearing potential just prior to randomization.
- ⁹ Clinical safety labs include hematology, blood chemistry, and urinalysis at all visits. Coagulation is included at Screening (Visit S1) for all patients, Baseline (Visit T1) and 3-5 days after Visit T1 only if on anticoagulants). Please refer to laboratory manual for detailed schedule of tests. A local laboratory may be used for assessment at 3-5 days after Visit T1.
- ¹⁰ Basic fasting (minimum of 10 hours) lipids include total cholesterol, calculated LDL-C, HDL-C, non-HDL-C, and triglycerides.
- ¹¹ Diet and exercise counseling per local and/or regional guidelines for the management of hyperlipidemia.
- ¹² IWRS contact at either an early withdrawal or an EOS visit to register study discontinuation visit date.
- ¹³ Depending upon the length of time between visits, 1 or 2 bottles of study medication will be dispensed as instructed by IWRS.
- ¹⁴ If patient is discontinuing treatment and completing the EOS visit, but will be continuing in the study either by returning to clinic or by phone, continue to schedule study visits for the patient according to the protocol Schedule of Events

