10.2.5. Treatment Week 4 (Visit T2; 29 ±3 days)

If the patient is withdrawing early from the study at this visit, proceed to [Section 10.3.2](#) for the list of the required assessments.

If the patient is withdrawing from IMP treatment at this visit, proceed to [Section 10.3.2](#) for the list of the required assessments. The patient will be asked to continue to be followed for safety using the protocol-specified visit schedule.

Patients refusing to continue to return to the clinic for protocol assessments after withdrawing from IMP treatment will be asked to participate in phone calls from the site at protocol-specified visits, or at a minimum at 52 weeks, to inquire about the patient's current health status and collect information on AEs (eg, recent procedures, hospitalizations, and if the patient has died, the cause of death). If the patient consents for telephone contacts, schedule the next protocol-specified visit.

Patients will undergo the following assessments and procedures at Week 4 (Visit T2):

- Concomitant and prohibited medication review (ongoing)
- Assess AEs, SAEs, and potential clinical endpoints since last visit (ongoing)
- Weight
- Vital signs

- Clinical laboratory evaluations:
 - Hematology, blood chemistry, and urinalysis
 - Basic fasting lipids (TC, calculated LDL-C, HDL-C, non-HDL-C, and TG)
- Conduct diet and exercise counseling
- Return of IMP; assessment and recording of IMP compliance
- Re-dispense IMP container from Visit T1 to patient for continued dosing and provide dosing instruction
- Schedule next visit

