10.2.6. Treatment Week 8 / Telephone Visit (Visit T3; 57 ±3 days)

Patients will undergo the following assessments via telephone at Week 8 (Visit T3):

- Concomitant medication review (ongoing)
- Assess AEs, SAEs, and potential clinical endpoints
- Diet and exercise counseling
- Assessment of study drug dosing adherence

Note: If the patient discontinues at or between study visits, please proceed to [Section 10.3.2](#) for detailed instructions.

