10.2.7. Treatment Week 12 (Visit T4; 85 ±3 days)

If the patient is withdrawing early from the study at this visit, proceed to [Section 10.3.2](#) for the list of the required assessments.

If the patient is withdrawing from IMP treatment at this visit, proceed to [Section 10.2.10](#) for the list of the required assessments. The patient will be asked to continue to be followed for safety using the protocol-specified visit schedule. If the patient consents for follow-up, schedule the next protocol-specified visit.

Patients who do not provide consent to continue to return to the clinic for safety assessments after withdrawing from IMP treatment will be asked to participate in phone calls from the site at protocol-specified visits, or at a minimum at 52 weeks, to inquire about the patient's current health status and collect information on AEs (eg, recent procedures, hospitalizations, and if the patient has died, the cause of death). If the patient consents for telephone contacts, schedule the next protocol-specified visit.

Patients will undergo the following assessments and procedures at Week 12 (Visit T4):

- Concomitant and prohibited medication review (ongoing)
- Assess AEs, SAEs, and potential clinical endpoints since last visit (ongoing)
- Weight
- Vital signs

- Clinical laboratory evaluations:
 - Hematology, blood chemistry, and urinalysis
 - Basic fasting lipids (TC, calculated LDL-C, HDL-C, non-HDL-C, and TG)
 - apoB
 - HbA_{1C}
 - hs-CRP
- Conduct diet and exercise counseling
- Return of IMP; assessment and recording of IMP compliance
- IWRS contact to obtain the MED ID number for IMP
- Dispense IMP and provide dosing instructions (one 100-day supply bottle)
- Schedule next visit

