10.2.10. Treatment Week 52/EOS (Visit T7; 365 ±7days)

Patients will undergo the following assessments and procedures at Week 52 (Visit T7), when completing an End of Study (EOS) visit, withdrawing from study (early withdrawal), or withdrawing from IMP treatment:

Patients will undergo the following assessments and procedures at Week 52 (Visit T7):

- Concomitant and prohibited medication review (ongoing)
- Assess AEs, SAEs, and potential clinical endpoints since last visit (ongoing)
- PE
- Weight
- 12-Lead ECG
- Vital signs
- Clinical laboratory evaluations:
 - Hematology, blood chemistry, and urinalysis
 - Basic fasting lipids (TC, calculated LDL C, HDL C, non-HDL C, and TG)
 - apoB
 - HbA_{1C}

- hs-CRP
- PK sample before dose
- Return of IMP; assessment and recording of IMP compliance
- Complete study status in IWRS (ie, early withdrawal or completed study).

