10.3. Subject Withdrawal Criteria

10.3.1. Early Withdrawal from the Study

Patients must remain in the study until the last scheduled visit at Week 52 (Visit T7) to be considered as having completed participation in the study.

Patients who withdraw from IMP prior to Week 52 (Visit T7) for any reason will be asked to continue to be followed for safety assessments, including basic fasting lipids, at clinic visit following the protocol-specified visit schedule (see [Appendix 1](#)).

Patients who temporarily withdraw from IMP prior to Week 52 (Visit T7) for any reason may restart IMP providing that 1) the patient and the investigator are in agreement regarding this course of action, 2) the patient has been off of IMP for 4 weeks or less; and 3) IMP can be started as soon as possible. For cases where the patient has been off of IMP for more than 4 weeks, the investigator must contact the medical monitor for approval prior to restarting IMP.

Patients who refuse to continue to return to the clinic for safety assessments will be asked to participate in phone calls from the site at protocol-specified visits (see [Appendix 1](#)), or at a minimum at 52 weeks, to collect information on AEs, concomitant medications, and current health status. The patient must provide consent to be contacted by phone by site personnel for the purposes of assessing current AEs and current health status.

The patient's decision to participate in the clinical study is voluntary. Patients may refuse to continue in the study and/or withdraw from participation in this study at any time, for any reason, specified or unspecified, and without penalty or loss of benefits to which the patient is otherwise entitled.

It is the right and duty of the Investigator to interrupt the treatment of any patient whose health or well-being may be threatened by continuation in this study. Such patients should be withdrawn from the study and should not be continued under a modified regimen.

Patients who are withdrawn from the study may not re-enter. The reasons for withdrawal from this study may include:

- Patient's withdrawal of consent
- Failure to comply with the protocol
- Lost to follow-up
- Illness, condition, or procedural complication (including AEs) affecting the patient's ability to participate or requiring prohibited medication
- The Sponsor or Investigator terminates the study

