10.3.2. Procedures for Early Withdrawal

If a patient withdraws or is removed from the study for any reason, all End of Study procedures should be completed. Reason for withdrawal, date of the discontinuation, and date of the last dose of study drug should be recorded in the appropriate section of the eCRF. Additionally, the discontinuation visit date must be registered in IWRS. Study drug assigned to the withdrawn patient may not be assigned to another patient.

All effort should be made to have each patient complete all study visits on schedule according to the protocol. Accommodations for early or late visits in special circumstances will be considered by the Sponsor to prevent early withdrawal. Written notice (regardless of cause) is to be provided within 48 hours of the withdrawal to the Sponsor personnel or the Medical Monitor. At the time of discontinuation, every effort should be made to ensure all relevant procedures and evaluations scheduled for the final study visit are performed. Except in the case of a medical emergency, the procedures and assessments detailed in [Section 10.2.10](#) will be performed upon the discontinuation of the study.

Patients choosing to withdraw from the study early should be encouraged to return for all study scheduled clinic visit even if they are no longer taking IMP. Patients who withdraw from all aspects of the study will be asked to consent to clinical visits or phone calls for safety assessments, including AEs, concomitant medication, and current health status through Week 52 (Visit T7).

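### Appendix 1 exempts apoB and hs-CRP after patients stop study drug, other protocol text does not, and two alpha-controlled Week 12 endpoints may lose obtainable values

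*Protocol*

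**What the plan says.** **Text that exempts the two assays.** The NOTE under the Appendix 1 schedule keeps patients who stop study drug on the visit schedule and then states: "Safety assessments should include clinical safety and basic lipid laboratories (except for apoB and hs-CRP), adverse events, PE, vital signs, and ECGs". Section 10.3.1 says such patients "will be asked to continue to be followed for safety assessments, including basic fasting lipids" and refers to Appendix 1. Footnote 10 of Appendix 1 reads: "Basic fasting (minimum of 10 hours) lipids include total cholesterol, calculated LDL-C, HDL-C, non-HDL-C, and triglycerides". ApoB and hs-CRP are not in that list.

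**Text that does not.** The synopsis has patients who stop drug followed on the scheduled visits with the scheduled procedures. Section 10.2.7 lists both assays at Week 12, and the T4 column of the schedule marks both. None of these makes an exception for patients off drug.

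**Withdrawal bloods.** Section 10.2.10, which includes both assays, applies "when completing an End of Study (EOS) visit, withdrawing from study (early withdrawal), or withdrawing from IMP treatment". SAP Section 6.4 assigns a sample to Week 12 if it is collected on Days 72 to 127.

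**Use of the data.** Week 12 apoB and hs-CRP are steps 5 and 6 of the hierarchy (Protocol 12.6, SAP 7.5), analysed in all randomized patients. Protocol 12.6 and SAP 17.2.1 apply the primary endpoint's imputation to the step-down endpoints. SAP 17.1.3 imputes patients who are off treatment from placebo data.

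**The concern.** The efficacy analyses follow the randomized group regardless of treatment actually taken, so off-drug values at Week 12 are wanted. A patient who stopped early and still attends Week 12 gives fasting blood at that visit. Steps 1 to 4 of the hierarchy can use that patient's measurements. If the NOTE is followed, steps 5 and 6 cannot, and the gap is created by the protocol rather than by the patient.

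For a bempedoic acid patient, apoB is then generated from placebo patients, using stratum and baseline (SAP Appendix 4). For hs-CRP, the SAP specifies a Wilcoxon test with a Hodges-Lehmann estimate, while Appendix 4 describes combining ANCOVA results only. The patient is therefore either imputed with no stated pooling method or left out.

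The supporting analyses do not recover the data. The observed-case analysis (SAP 17.2.3.4), the tertiary Week 24 and Week 52 analyses (SAP 17.3.2) and the analysis of hs-CRP below 2 mg/L all use observed data only. Off-drug patients with no in-window value simply drop out of them. For these two markers, that moves the observed-case analysis toward the on-treatment one.

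**Working it through.** **Plan's own figure.** With 500 and 250 patients, a difference of 15 and an SD of 15, the noncentrality is 15 / (15 × √(1/500 + 1/250)) = 12.91. Power exceeds 0.999, which agrees with the stated figure of more than 95%. That figure is for LDL-C and this point does not alter it.

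**Who is affected.** Withdrawal bloods drawn from Day 72 on supply a Week 12 value. The gap is confined to patients whose withdrawal bloods precede Day 72 and who then attend Week 12. The earliest scheduled Week 12 visit is Day 82 (85 − 3). Since 82 − 7 = 75 is later than Day 71, anyone who stopped for good by Day 71 is off treatment under SAP 17.1.3.

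**When the withdrawal bloods are drawn.** The protocol does not settle this.
- Section 10.2.5 ties them to a clinic visit: "If the patient is withdrawing from IMP treatment at this visit, proceed to" the withdrawal assessments. No clinic visit is scheduled between Day 29 and Day 85, so on this reading only stops on Days 1 to 29 are lost.
- Section 10.2.6 says "If the patient discontinues at or between study visits, please proceed to" Section 10.3.2, which says: "At the time of discontinuation, every effort should be made to ensure all relevant procedures and evaluations". On this reading, stops on Days 1 to 71 are lost.

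**Number of patients.** Rates of stopping and attendance are assumptions. Sets A and B take 5% to 10% stopping before Week 12, evenly over Days 1 to 84, with 50% to 100% attending. Set C takes 2% to 10% stopping before Day 72, with 25% to 75% attending. Two thirds are on bempedoic acid.

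| Set | Low | High | Share of 750 | On bempedoic acid |
|---|---|---|---|---|
| A: bloods at next clinic visit | 37.5 × 29/84 × 0.5 = 6.5 | 75 × 29/84 × 1 = 25.9 | 0.86% to 3.45% | 4.3 to 17.3 |
| B: bloods at time of stopping | 37.5 × 71/84 × 0.5 = 15.8 | 75 × 71/84 × 1 = 63.4 | 2.11% to 8.45% | 10.6 to 42.3 |
| C: direct rates | 750 × 0.02 × 0.25 = 3.75 | 750 × 0.10 × 0.75 = 56.25 | 0.5% to 7.5% | 2.5 to 37.5 |

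The overall range is about 4 to 63 patients.

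**Effect on the apoB difference.** Shift = share of the bempedoic acid arm affected × (true off-drug mean minus imputed mean), with no gap in the placebo arm.
- Set A, assumed gap of 5 to 10 points: 0.0086 × 5 = 0.04 to 0.0345 × 10 = 0.35 points.
- Set B, same gap: 0.0211 × 5 = 0.11 to 0.0845 × 10 = 0.85 points.
- Set C, with 0% to 50% of an assumed 15-point effect persisting off drug: 0 to 0.075 × 0.5 × 15 = 0.56 points.

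The documents give no basis for any of these gaps. At the longest half-life in Protocol 4.2.3 (33 hours), the fraction left after 10 days is 0.5^(240/33) = 0.6%, so the true gap may be near zero. No size can be given for hs-CRP, for which the documents state neither an expected effect nor a spread.

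**The case against.** The strongest objection is that the exemption may not be operative. The NOTE is worded as guidance on safety assessments. It names physical examination and ECG, which the schedule places only at T1 and T7, so it is not a literal Week 12 list. Section 10.3.1 is not worded exclusively, and footnote 10 only defines basic lipids. Section 11.7.1 even has apoB analysed at every clinic visit, which is more than the schedule provides. As context only, the amendment history shows a similar exception struck from the Week 12 section while the NOTE kept its own, so intent is unclear. This objection stands in part. A reader might infer that the plan settles on not collecting the assays, and the documents do not support that. But footnote 10 already leaves both assays out of basic lipids, so the parenthesis in the NOTE has no function except to exclude them, and sites can reasonably follow it.

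A second objection is that placebo-based imputation of off-drug bempedoic acid patients is the SAP's declared assumption and is conservative if some effect persists. That also stands. The same patients' measured lipids give an indirect check of the assumption for apoB, though they say little about hs-CRP. Imputing placebo withdrawals from placebo data is no concern. None of this helps the observed-only analyses, where the patients disappear.

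**Conclusion.** The point holds as a conflict between protocol passages with an avoidable, conditional loss of data. If sites follow the NOTE, some early withdrawals who attend Week 12 lack apoB and hs-CRP while their other lipids are observed. The size, about 4 to 63 of 750 patients and under 1 percentage point on the apoB difference, rests wholly on assumed withdrawal and attendance rates and an assumed off-drug gap.

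Three stronger readings are not supported:
- **All withdrawn patients lose these values.** They do not: withdrawal bloods include both assays and count as Week 12 from Day 72.
- **Both endpoints are certain to be imputed.** That is firm for apoB. For hs-CRP the general rule points to imputation, but how it would work with the rank test is not stated.
- **The error rate or power is compromised.** The patients stay in the Full Analysis Set, the sequence and alpha are unchanged, and stated power is unaffected.

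This is a cheap improvement, not a threat to the trial's conclusions.

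**What to change.** In the Appendix 1 NOTE, replace the parenthesis excluding apoB and hs-CRP with wording that adds both assays at Weeks 12, 24 and 52. Align Section 10.3.1 with the synopsis and Section 10.2.7. Week 12 is what the hierarchy needs; Weeks 24 and 52 protect the tertiary analyses, which have no imputation.

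A reader might think that no SAP change follows, but one does. Appendix 4 imputes on-treatment bempedoic acid patients (cohort 2) from cohorts 6 and 8, and cohort 8 is bempedoic acid patients observed off treatment. Section 17.1.3 says those values should resemble patients who remain on treatment. Collecting more off-drug values would enlarge cohort 8 and feed them into on-drug imputation. Limit the donors for cohort 2 to cohort 6, in both the table and the code.

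The cost is a short protocol amendment, a small SAP edit, and two extra assays per attended visit for withdrawn patients. No visit is added. One more tube may be needed, which depends on the laboratory manual.
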